9.5.2. Data Management

The CRO will be responsible for activities associated with the data management of this study. The standard procedures for handling and processing records will be followed per GCP and the CRO's standard operating procedures (SOPs). A comprehensive Data Management Plan will be developed including a data management overview, database contents, annotated CRF and consistency checks.

Study site personnel will be responsible for providing resolutions to all data queries. The investigator will be required to document electronic data review to ensure the accuracy of the corrected and/or clarified data.

The sponsor will review all data reported in CRFs of all patients before database lock. The data review meeting determines whether or not all enrolled patients can be included in the analysis

population according to the specified definition of analysis populations and evaluates whether or not medical decisions of the Investigator were appropriate for important data affecting the safety and efficacy endpoint.

9.5.3. Quality Assurance/Audit

This study will be subject to audit by the sponsor, CRO, or designee.

The sponsor or sponsor's representative may conduct audits on a selection of study sites, requiring access to patient notes, study documentation, and facilities or laboratories used for the study.

The study site, facilities, all data (including source data), and documentation will be made available for audit by quality assurance auditors and for IRB or regulatory authorities according to GCP guidelines. The investigator agrees to cooperate with the auditor during the visit and will be available to supply the auditor with CRFs or other files necessary to conduct that audit. Any findings will be strictly confidential.

If a regulatory authority informs the investigator that it intends to conduct an inspection, the investigator shall notify sponsor or sponsor's representative immediately.

9.6. Study Termination

The study may be terminated at the sponsor's discretion at any time and for any reason. Study sites may be asked to have all patients currently participating in the study complete all of the assessments for the telephone follow-up call.

In the event of study discontinuation, study sites may be asked to have all patients currently participating in the study complete all of the assessments for the Early Withdrawal Visit.

9.7. Study Site Closure

At the end of the study, all study sites will be closed. The sponsor or sponsor's representative may terminate participation of a study site at any time. Examples of conditions that may require premature termination of a study site include, but are not limited to, the following:

- Noncompliance with the protocol and/or applicable regulations and guidelines.
- Inadequate patient enrollment.

9.7.1. Record Retention

The investigator shall retain and preserve one copy of all data generated in the course of the study, specifically including, but not limited to, those defined by GCP as essential until the following occur:

- At least 2 years after the last marketing authorization for the investigational product (IP) has been approved or the sponsor has discontinued its research with the IP, or
- At least 2 years have elapsed since the formal discontinuation of clinical development of the IP

These documents should be retained for a longer period, however, if required by the applicable regulatory requirement(s) or if needed by the sponsor.

Insys will keep personal data for no longer than reasonably necessary for our ongoing course of study, regulatory filing, and for record keeping purposes and in case of any legal claims of complaints.

Furthermore, EU citizens of residents have the following rights under the GDPR (unless subject to an exemption):

- The right to request a copy of your personal data which Insys holds about you
- The right to request that Insys corrects any personal data if it is found to be inaccurate or out of date
- The right to request your personal data is erased where it is no longer necessary for Insys to retain such data
- The right to withdraw your consent to the processing at any time
- The right to request that Insys provide you, as the data subject, with your personal data and where possible, to transmit that data directly to another data controller
- The right, where there is a dispute in relation to the accuracy or processing of your personal data, to request a restriction is placed on further processing
- The right to lodge a complaint with governmental agencies or Data Protection Authorities as provided for in the GDPR.

9.7.2. Pharmacokinetic/Laboratory Sample Retention

Laboratory samples may be used for purposes related to this research. The samples will be stored until the sponsor has determined that specimens are no longer needed and the decision has been made that none of the samples needs to be reanalyzed. In addition, identifiable samples can be destroyed at any time at the request of the patient.

9.8. Changes to the Protocol

The investigator may not deviate from the protocol without a formal protocol amendment established and approved by the appropriate IEC/IRB, except when necessary to eliminate immediate hazards to the patient or when the change involves only logistical or administrative aspects of the study. Any deviation may result in patient withdrawal from the study and rendering that patient not available for data evaluation.

The Investigator or sub-investigator should document any deviation from the protocol and the reason. If the Investigator performs a deviation from the protocol or a change of the protocol to eliminate an immediate hazard(s) to patients, the record should be immediately submitted to the sponsor, the Clinical Research Unit (CRU), and the IRB by the Investigator. The IRB will provide expedited review and approval. After the Investigator has obtained approval of the IRB, the Investigator should obtain written permission of the CRU and written agreement of the sponsor.

9.9. Financial Disclosure

These issues will be addressed in a separate agreement between the sponsor and the Investigator. The US FDA Financial Disclosure by Clinical Investigators (21 Code of Federal Regulations [CFR] 54) regulations require sponsors to obtain certain financial information from investigators

participating in covered clinical studies; each investigator and sub-investigator is required to provide the required financial information and to promptly update Insys Development Company, Inc., with any relevant changes to their financial information throughout the course of the clinical study and for up to one year after its completion. This rule applies to all investigators and sub-investigators participating in covered clinical studies to be submitted to the FDA in support of an application for market approval.

10. REGULATORY AND ETHICAL CONSIDERATIONS

10.1. Regulatory Authority Approval

The investigator will ensure that the protocol and consent forms are reviewed and approved by the appropriate Independent Ethics Committee/Institutional Review Board (IEC/IRB) prior to the start of any study procedures. The IEC/IRB will be appropriately constituted and will perform its functions in accordance with Food and Drug Administration (FDA) regulations, International Conference on Harmonization (ICH) good clinical practice (GCP) guidelines, and local requirements as applicable.

In addition, the IRB will approve all protocol amendments (except for logistical or administrative changes), written informed consent documents and document updates, patient recruitment procedures, written information to be provided to the patients, available safety information, information about payment and compensation available to patients, the investigator's curriculum vitae and/or other evidence of qualifications, and any other documents requested by the IRB/IEC and regulatory authority, as applicable.

The Investigator will supply documentation to the Sponsor or designee of required IRB/IEC annual renewal of the protocol, and any approvals of revisions to the consent form, or amendments to the protocol.

10.2. Ethical Conduct of the Study

The study will be conducted in accordance with the Declaration of Helsinki and GCP according to ICH guidelines. Specifically, the study will be conducted under a protocol reviewed by an IRB or IEC; the study will be conducted by scientifically and medically qualified persons; the benefits of the study are in proportion to the risks; the rights and welfare of the patients will be respected; the physicians conducting the study do not find the hazards to outweigh the potential benefits; and each patient will give his or her written, informed consent before any protocol-driven tests or evaluations are performed.

10.3. Statement of Investigator/Delegation of Authority

As a condition for conducting the clinical investigation, the Principal Investigator will sign the FDA Form 1572, Statement of Investigator (21 Code of Federal Regulations [CFR] Part 312).

The Principal Investigator will ensure that all persons assisting with the trial are adequately qualified, informed about the protocol, any amendments to the protocol, the study treatments, and their trial-related duties and functions. The qualified investigator will maintain a list of sub-investigator and other appropriately qualified persons to whom to delegate significant trial-related duties. Should the qualified investigator delegate the supervision of the investigational product administration to a designated person, this individual must have the appropriate medical qualifications to effectively conduct or supervise any potential resuscitation procedures.

10.4. Patient Informed Consent

The Investigator is responsible for ensuring that informed consent is obtained from each parent/caregiver or legal representative and for obtaining the appropriate signatures and dates on

the consent form form (if applicable) prior to the performance of any protocol procedures and prior to the administration of study medication.

The investigator or his/her designee will inform the parent/caregiver or legal guardian of all aspects pertaining to their participation in the study. The process for obtaining informed consent will be in accordance with all applicable regulatory requirements (e.g., CFR Part 50 and ICH E6 Section 4.8). The investigator or his/her designee and the parent/caregiver or legal guardian must both sign and date the informed consent document (ICD) before the patient can participate in the study. The parent/caregiver or legal guardian will receive a copy of the signed and dated form, and the original will be retained in the site's study records. The decision to participate in the study that is made by the parent/caregiver or legal guardian is entirely voluntary. The investigator or his/her designee must emphasize to the parent/caregiver or legal guardian that consent for study participation may be withdrawn at any time without penalty or loss of benefits to which the patient is otherwise entitled. If the ICD is amended during the study the investigator must follow all applicable regulatory requirements pertaining to approval of the amended ICD by the IEC/IRB, and use of the amended form, including the necessity of re-consenting ongoing patients.

10.5. Investigator Reporting Requirements

In accordance with applicable local regulatory requirements, the investigator may be obligated to provide periodic safety updates on the conduct of the study at his/her site and notification of study closure to the IRB. Such periodic safety updates and notifications are the responsibility of the investigator and not of Insys or its delegate.

11. USE OF INFORMATION AND PUBLICATION POLICY**11.1. Use of Information**

All information concerning Cannabidiol Oral Solution and Insys Development Company's operations, such as Insys' patent applications, formulas, manufacturing processes, basic scientific data, or formulation information, supplied by Insys Development Company and not previously published, is considered confidential information.

This confidential information shall remain the sole property of Insys Development Company, shall not be disclosed to others without the written consent of Insys Development Company, and shall not be used except in the performance of this study.

The investigator will maintain a confidential patient identification code list of all patients enrolled in the study (by name and patient number). This list will be maintained at the site, and will not be retrieved by Insys.

11.2. Publication Policy

Insys Development Company, Inc. will retain ownership of all data. All proposed publications based on this study will be subject to the sponsor's approval requirements.

APPENDIX 1. CYP3A4-RELATED PROHIBITED MEDICATIONS

Example of prohibited medications (list is not exhaustive).

1. Strong inhibitors

- Boceprevir
- Clarithromycin
- Conivaptan
- Valproic acid
- Grapefruit juice
- Indinavir
- Itraconazole
- Ketoconazole
- Lopinavir/ritonavir
- Mibefradil
- Nefazodone
- Nelfinavir
- Posaconazole
- Saquinavir
- Telaprevir
- Telithromycin
- Voriconazole

2. Strong inducers

- Avasimibe
- Carbamazepine
- Phenobarbital
- Phenytoin
- Rifampin
- St. John's Wort

3. Sensitive substrates with a narrow therapeutic index

- Alfentanil
- Astemizole
- Cisapride

- Cyclosporine
- Dihydroergotamine
- Ergotamine
- Fentanyl
- Pimozide
- Quinidine
- Sirolimus
- Tacrolimus
- Terfenadine

## TECHNICAL SUMMARY REPORT (TSR)

Name of Sponsor/Company {Sponsor Name}	Individual Study Table Referring to Part of the Dossier: Volume:	(For National Authority Use Only):
Name of Investigational Product: Cannabidiol Oral Solution	Page:	
Name of Active Ingredient: Cannabidiol		
Title of Study: A Phase 3 Randomized, Double-Blind, Placebo-Controlled, Parallel-Group Study to Assess the Efficacy, Safety, and Tolerability of Cannabidiol Oral Solution as Adjunctive Therapy with Vigabatrin as Initial Therapy in Infants with Infantile Spasms		
Investigators: Approximately 35 sites in the US, Canada, and Australia.		
Studied period (years): Estimated Date of first patient in (FPI): Estimated Date of last patient in (LPI):	Phase of development: 3	

Objectives:
 
Primary:
 
 
To evaluate the efficacy of Cannabidiol Oral Solution as adjunctive therapy with vigabatrin as initial therapy in treating patients with Infantile Spasms.
 
 
Secondary
 
 
to evaluate the continued efficacy of the combination treatment of Vigabatrin plus CBD after the initial 14 days.
 
To evaluate the safety and tolerability of Cannabidiol Oral Solution as adjunctive therapy with vigabatrin as initial therapy in treating patients with Infantile Spasms.
 
		

### **Methodology:**

This is a Phase 3, double-blind, placebo-controlled, randomized, multicenter study to evaluate the efficacy, safety, and tolerability of Cannabidiol Oral Solution (CBD) as adjunctive therapy with Vigabatrin as initial therapy, compared to Vigabatrin alone in the treatment of infants newly diagnosed with Infantile Spasms (IS). Randomization will be stratified by developmental impairment (high or low) as determined by the investigator during Screening Visit 1 and then allocated to one of two treatment groups:

- Treatment with vigabatrin *plus*
  - CBD 40 mg/kg/day, or
  - Matching CBD 40 mg/kg/day placebo

One hundred eighty patients in total will be enrolled into one of the two treatment arms: 120 patients in the investigational product arm and 60 patients in the placebo arm. Patients will be dosed approximately every 12 hours with food to help ensure consistent plasma levels are achieved.

In addition to the safety assessments required by the study protocol, the investigator will monitor patients throughout the study as recommended in the current approved product label for Vigabatrin. Study participants will be newly diagnosed pediatric patients age 3 to 12 months (inclusive) experiencing infantile spasms who satisfy all inclusion/exclusion criteria. This study will be comprised of five periods: Screening, Initial Treatment, Extended Treatment, Taper, and Follow-up Periods, with a maximum duration of approximately 137 days.

Each newly diagnosed patient with Infantile Spasms will complete a Screening Period for up to 14 ( $\pm$  5) days.

Patients will have an overnight, minimum of a 9-hour video-EEG that includes at least one full sleep-wake cycle during their Screening Visit to establish their baseline level of infantile spasms and hypsarrythmia or a pattern of epileptic encephalopathy, and a 24-hour video-EEG at Visit 4 (Day 13) of the Initial Treatment Period to establish their final level of infantile spasms and hypsarrythmia. During the Extended Treatment Period, a 9-hour video-EEG will be conducted to confirm parent/caregiver report of relapse or resolution.

#### Initial Treatment Period

At the Baseline Visit (Visit 2, Day 1), patients will receive the titration dose of Vigabatrin (50 mg/kg/day divided twice daily [BID]), and either CBD 20 mg/kg/day plus matching CBD 20 mg/kg/day placebo or CBD 40 mg/kg/day placebo, each drug administered twice daily for three days.

On Day 4 (Visit 3), patients will return to the study center to evaluate medical status (seizure diary, vital signs, and neurological exam), clinical laboratory assessments, and assess adverse events (AEs), then increase Vigabatrin to 100 mg/kg/day, and CBD or matching CBD placebo to 40 mg/kg/day for 11 days. Vigabatrin, CBD, and matching placebo will be administered in a twice daily fashion at 12-hour intervals. As part of their standard of care, the investigator will assess safety and tolerability during the first three days of the Initial Treatment Period.

Patients will be dosed for a total of 14 days during which the investigator will assess tolerability and efficacy.

#### Extended Treatment Period

Following the Initial Treatment Period, Complete and Partial Responders in the treatment arm will continue receiving CBD 40 mg/kg/day and Vigabatrin for 76 days, until Week 13 (Day 90) to monitor progress for treatment response. Complete and Partial Responders in the placebo arm will continue receiving Vigabatrin during the Extended Treatment Period. Non-responders will be tapered off Vigabatrin and CBD as specified in the Protocol.

#### Taper Period

Following the completion of the Initial Treatment Period (Visit 5), all non-responders receiving Vigabatrin will be tapered off. Similarly, all non-responders receiving CBD will be tapered off according to the protocol. Patients will also be tapered off Vigabatrin and CBD at the completion of the Extended Treatment Period or at Early Withdrawal Visits.

#### Follow-up Period

A follow-up phone call will occur 30 days after discontinuation of the study drug to assess AEs, AEDs, and record concomitant medications.

#### Study Assessments

To assess efficacy, a 9-hour video-EEG that includes at least one sleep-wake cycle, a 24-hour video-EEG, daily seizure diaries, and investigator Clinical Global Impressions-Global Improvement (CGI-I) assessments will be completed and evaluated.

- A 9-hour video EEG that includes at least one sleep-wake cycle will be completed during Screening (Visit 1) and a 24-hour video EEG will be completed at Visit 5.
- Daily seizure diaries will be completed throughout the Initial and Extended Treatment Periods. The daily record will ask: "How many spasms did the patient have today?"
- The CGI-I will be completed by the investigator at Visit 5 of the Initial Treatment Period, or at Early Withdrawal.

Safety assessments for all patients will include medical history, physical examination, vital signs (seated blood pressure, pulse rate, temperature, and respiration rate), clinical laboratory testing (hematology, chemistry, and urinalysis), prior medication history (assessment of past/current AEDs and concomitant medications), and AE assessments will be conducted at specific visits throughout the study.

If a patient discontinues the study prematurely, the parent's impression of efficacy and tolerability of the study drug, as evaluated by CGI-I, will be assessed and recorded immediately before discontinuation. If possible, the parent/caregiver will be encouraged to have the patient have an Early Withdrawal video-EEG completed.

#### **Number of patients (planned):**

Approximately 180 patients (120 patients in the active drug arm and 60 patients in the placebo arm).

**Diagnosis and main criteria for inclusion:**

Patients will be male and female patients between 3 and 12 months of age (inclusive), with a new clinical diagnosis of Infantile Spasms, confirmed by video-EEG analysis during the Screening Period, have adequate renal and hepatic function and who meet all the inclusion and none of the exclusion criteria. Parent(s)/caregiver(s) must be able to understand and provide written consent.

**Investigational product, dosage, and mode of administration:**

Cannabidiol Oral Solution or Placebo (IP). Initial dose of the IP will be either matching CBD placebo 20 mg/kg/day or CBD 20 mg/kg/day for 3 days, after which the dose of IP will be adjusted to the final dose of CBD or CBD placebo 40 mg/kg/day divided twice daily for 11 days, manufactured for and supplied by Insys Development Company, Inc. Following the completion of the 14-day Initial Treatment Period, Complete and Partial Responders will receive CBD 40 mg/kg/day for 76 days during the Extended Treatment Period.

**Duration of treatment:**

The maximum duration of the study from screening to follow-up of AEs will be approximately 144 days.

**Reference therapies, dosage and mode of administration:**

Vigabatrin powder suspension divided twice daily with food, 50 mg/kg/day for 3 days, then 100 mg/kg/day for 11 days.

**Criteria for evaluation:**

**Efficacy**

Primary efficacy endpoint

- Percent of patients who are considered complete responders, defined as complete resolution of spasms and hypsarrhythmia or a pattern of epileptic encephalopathy confirmed by 24-hour video-EEG from Day 13 to Day 14, as determined by the Independent Central Reader.

Secondary efficacy endpoints

- Percent of patients with resolution of infantile spasms as assessed by 24-hour video-EEG from Day 13 to Day 14 (partial response).
- Percent of patients with resolution of hypsarrhythmia or pattern of epileptic encephalopathy as assessed by 24-hour video-EEG from Day 13 to Day 14 (partial response).
- Investigator impression of efficacy and tolerability of study drug (CGI-I) at Visit 5 (End of Study) or Early Withdrawal.
- Percent reduction in spasm-free days between the Initial Treatment Period (Days 1 to 14) and Screening Period (Days -14 to -1), as determined by the seizure diary entries.
- For patients with a complete response during the Initial Treatment Period who continue: percent of patients who relapse during the Extended Treatment Period confirmed by video-EEG following parent report of relapse, and time to relapse.
- For patients with partial response during the Initial Treatment Period who continue: percent of patients who achieve complete response during the Extended Treatment Period, confirmed by video-EEG following parent report, and time to complete response.

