Patients will have a, minimum of a 9-hour video EEG that includes at least one full sleep-wake cycle during their Screening Visit to establish their baseline level of infantile spasms and hypsarrythmia and a 24-hour video EEG at Visit 5 (Day 14 to Day 15) of the Initial Treatment Period to establish their final level of infantile spasms and hypsarrythmia. A blinded central reader, not involved in the study, will evaluate the video EEGs and determine responder status. Details of the video EEG assessment will be provided in the video-EEG Charter. The treatment response categories are summarized in [Table 2](#). In addition, a 9-hour video EEG will be conducted during the Extended Treatment Period to confirm parent/caregiver report of relapse. If possible, a 9-hour video EEG will be conducted for patients who have continued into the Extended Treatment Period and decided to Early Withdraw. A video EEG is not required for patients who decide to withdraw during the Initial Treatment Period.

Table 2: Video EEG Response Definitions

Response Category	Definition
Complete Response	Complete resolution of spasms and hypsarrythmia confirmed by video EEG
Partial Response	Complete resolution of either spasms or hypsarrythmia confirmed by video EEG
Non-Response	No improvement or worsening of spasms/hypsarrythmia burden

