8.1. Study Endpoints

8.1.1. Primary Efficacy Endpoint

The primary efficacy endpoint in this study is:

- Percent of patients who are considered complete responders, defined as complete resolution of spasms and hypsarrhythmia, confirmed by 24-hour video EEG from Day 14 to Day 15, as determined by the Independent Central Reader.

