8.4.3. Efficacy Analyses

A 9-hour video EEG will be conducted during the Screening Period (Baseline) and a 24-hour video EEG will be conducted from Day 14 to Day 15 of the Initial Treatment Period. In addition, to confirm parent/caregiver report of relapse or complete resolution a 9-hour video EEG will be conducted during the Extended Treatment Period. For each video EEG, the number of spasms will be counted and the presence of hypsarrhythmia determined. Change from Baseline for each measure will be summarized by the median difference. Patients will be defined as having Complete Response, Partial Response, or Non-Response on Day 15 as defined in [Table 2](#), the percentage of patients who achieve a Complete Response and Partial Responders in each treatment arm will be compared using a chi-square test.

The results of the CGI-I assessments will be listed and summarized by descriptive statistics as appropriate. The responses to the seizure diary will also be summarized by dose level and scheduled time point. All efficacy summaries will be based on the ITT Population.

Details of these summaries will be provided in the SAP. For all inferential statistical tests, a 2-sided type I error rate of 0.05 will be used throughout.

For the secondary efficacy endpoints, to maintain the trial-wise type I error rate at 0.05, a fixed sequence multiple comparisons correction with fallback will be used. The assignment of alpha levels to hypotheses being tested will be specified in the SAP.

For endpoints that are continuous in nature number, the number of observations, mean, median, minimum and maximum, and standard deviation (SD) values will be presented as descriptive statistics. For inferential statistics:

- If the normality assumption is met, analysis of covariance (ANCOVA) using the baseline value as a covariate will be used.
- If the normality assumption is not met, a rank-ANCOVA analysis i.e., an ANCOVA analysis on rank-transformed data or other non-parametric methods will be used.
- Time to event analyses will be described with Kaplan-Meier curves and treatment groups compared with log-rank tests.

For endpoints that are categorical in nature, frequency, counts, and percentages will be presented as descriptive statistics, and a chi-square test will be used for inferential statistics.

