### **5.2. Efficacy Assessments**

#### **5.2.1. Video-EEG**

Video-EEGs performed during the Screening Visit and Visit 4 to Visit 5 (Day 13 and Day 14), and during the Extended Treatment Period to confirm parent reports of relapse or seizure cessation. Data collected include: *Presence of spasms (Y/N), Number of spasms, and presence of Hypsarrhythmia (Y/N), presence of epileptic encephalopathy (Y/N).*

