##### **10.6.1. Primary Efficacy Analysis**

The primary efficacy endpoint in this study is:

- Percent of patients who are considered complete responders, defined as complete resolution of spasms and hypsarrhythmia or a pattern of epileptic encephalopathy.

The percent of complete responders will be calculated for each treatment group and compared using Fisher's exact test.

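### The SAP adds an undefined alternative EEG pattern to the primary endpoint that the protocol does not contain, so the same EEG findings can be classified differently under the two documents.

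*SAP*

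**What the plan says.** **Protocol.** Section 8.1.1 gives the primary endpoint as the percentage of complete responders, "defined as complete resolution of spasms and hypsarrhythmia, confirmed by 24-hour video EEG from Day 14 to Day 15", judged by the Independent Central Reader. The synopsis and Section 8.4.3.1 agree. So does Table 2 in Section 3.1: "Complete resolution of spasms and hypsarrythmia confirmed by video EEG". Section 8.4.3 says that for each video EEG "the number of spasms will be counted and the presence of hypsarrhythmia determined". Entry (Section 3.2.1, criterion 3) requires hypsarrhythmia on a centrally read EEG. The protocol text never mentions a pattern of epileptic encephalopathy.

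**SAP.** The Technical Summary Report (TSR) requires "complete resolution of spasms and hypsarrhythmia or a pattern of epileptic encephalopathy confirmed by 24-hour video-EEG from Day 13 to Day 14". Section 10.6.1 repeats the rule: "defined as complete resolution of spasms and hypsarrhythmia or a pattern of epileptic encephalopathy". The TSR primary analysis, Section 9.7 and Section 10.3.1 carry the same added term. Section 5.2.1 records hypsarrhythmia and epileptic encephalopathy as two separate yes/no items (the latter as "presence of epileptic encephalopathy (Y/N"). Entry under Section 3.2.1, criterion 3, is met by either pattern, read by the investigator.

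Section 1 of the SAP says that it is based on the protocol dated 30 October 2017. It adds that the SAP may change with amendments and must be final before database lock.

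**The concern.** This is the primary endpoint, and the two documents do not define the same event. The SAP itself treats the two EEG patterns as distinct, since it collects them separately, so the added words can change who counts as a responder. A programmer working from the SAP would also need a variable that the protocol does not ask the reader to supply. The word joining the two patterns is never explained, so the SAP rule cannot be applied without a further decision. If the SAP were finalised as it stands, that decision would be made outside both documents, or after someone had seen what it does to the result.

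**Working it through.** No figure in the plan depends on this point, so the check is a comparison of definitions.

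**Step 1: the rules.** Let H be hypsarrhythmia and E the other encephalopathic pattern. Read resolution as absence at follow-up, as SAP Section 10.3.2 does for the secondary endpoints. All rows below assume no spasms at follow-up.

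- Protocol: H absent.
- SAP reading (a): H and E both absent.
- SAP reading (b): at least one of H and E absent.
- SAP reading (c): the pattern present at baseline is absent.

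**Step 2: apply them to the same findings.**

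| Baseline | Follow-up | Protocol | SAP (a) | SAP (b) | SAP (c) |
|---|---|---|---|---|---|
| H only | neither | yes | yes | yes | yes |
| H only | E only | yes | no | yes | yes |
| H only | H only | no | no | yes | no |
| H and E | E only | yes | no | yes | not settled |
| H and E | H only | no | no | yes | not settled |
| E only (SAP entry only) | E only | yes | no | yes | no |

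Reading (a) is stricter than the protocol and reading (b) is looser. Reading (c) matches the protocol in all three rows with H alone at baseline. It is undetermined when both patterns were present at baseline, and it differs when only E was present.

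**Step 3: does the SAP say which reading applies?** No, and its own text pulls in different directions.

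- The entry criterion uses the same phrase, and the Section 10.3.2 null hypothesis for the EEG-pattern secondary endpoint refers to the pattern at baseline. Both favour (c).
- The matching alternative hypothesis drops E, and moves from Days 13-14 to Days 14-15.
- The design summary (TSR and Section 3.1) names E for the baseline EEG but only hypsarrhythmia for the final EEG.
- The table list in Section 14.2 names only hypsarrhythmia for that secondary endpoint.

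**Step 4: illustration of size, reading (a) only.** The share q of protocol responders who keep E is not in the documents. Assume the same q in both arms and multiply each response rate by (1 − q). The normal approximation to the power of the two-sided 0.05 chi-square test is Φ((|p1 − p2| − 1.96·s0)/s1), where s0 and s1 are the pooled and unpooled standard errors.

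- Protocol, 130 versus 60, 60% versus 40%: (0.20 − 1.96 × 0.0778)/0.0765 = 0.62, so 73.3%.
- SAP, 120 versus 60, 62% versus 40%: (0.22 − 1.96 × 0.0787)/0.0772 = 0.85, so 80.3%.

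The SAP's stated 80% therefore reproduces with a chi-square test (77.3% with the Fisher's exact test it specifies). The protocol's stated 80% does not, which is a separate issue. Exact enumeration for the chi-square test gives:

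| q | Protocol rates (%) | Power, 130:60 | SAP rates (%) | Power, 120:60 |
|---|---|---|---|---|
| 0% | 60 / 40 | 73.0% | 62 / 40 | 80.4% |
| 5% | 57 / 38 | 68.7% | 58.9 / 38 | 76.2% |
| 10% | 54 / 36 | 64.3% | 55.8 / 36 | 71.7% |
| 15% | 51 / 34 | 59.6% | 52.7 / 34 | 66.9% |

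Under reading (b) the response rates would rise instead, so even the direction depends on a reading that the SAP does not choose.

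**The case against.** The strongest reply is that this is one symptom of an SAP that has not caught up with its protocol. The SAP names the 30 October 2017 protocol as its basis. The supplied protocol cites conference posters from December 2017, so it appears to be later. Age range, sample size, dosing, EEG days, primary test and multiplicity method differ as well, and the SAP says that it may evolve. This stands as an explanation. It does not remove the conflict, because neither passage is an amendment log and the SAP text as supplied would govern the analysis if finalised.

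The second reply is that the natural meaning is reading (c), under which a protocol-eligible patient with hypsarrhythmia alone is classified identically. That reading is plausible, and it rules out any claim that the definitions always disagree. But the SAP never states it, and it leaves patients with both patterns undecided.

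Third, the EEG Charter might settle the matter. It is not among the documents, so this cannot be judged. The protocol leaves the details of EEG conduct and reading to the Charter but states the endpoint itself.

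Fourth, a reader might infer that the endpoint could be chosen freely after unblinding. The documents do not support that: the SAP requires decisions before database lock and a blinded central reader determines response. The risk is an unresolved rule at lock, not a licence to choose.

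**Conclusion.** The point holds and should be settled before database lock. The protocol and the SAP give different primary endpoints wherever each states one, and the SAP's version can be read in at least three ways. Agreement is limited to the baseline-pattern reading in patients with hypsarrhythmia alone at baseline. This conclusion rests on the wording and on no numerical assumption.

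Two stronger conclusions are tempting and should not be drawn. A reader might infer that the SAP endpoint no longer matches the event behind the assumed 60% versus 40% response rates. Neither document says which EEG definition its rates came from, the SAP has its own 62% versus 40%, and the 40% control rate is the same in both. A reader might also take the power figures as an estimate of loss. They rest on an assumed retention share, equal in both arms, and on the strictest reading only, so they illustrate and nothing more.

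**What to change.** Before database lock:

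1. Replace the definition in every SAP statement of the primary endpoint (TSR endpoint and analysis, Sections 9.7, 10.3.1 and 10.6.1) with that of protocol Section 8.1.1: no spasms and no hypsarrhythmia on the 24-hour video EEG of Days 14-15, as determined by the Independent Central Reader.
2. Make the same change in the hypsarrhythmia secondary endpoint, including both hypotheses in Section 10.3.2.
3. If an epileptic encephalopathy pattern is read, report it as a separate descriptive variable.
4. Align the SAP entry criterion (Section 3.2.1) with the protocol's, and check the EEG Charter against the same definition.
5. State how any patient enrolled without baseline hypsarrhythmia is classified. Otherwise such a patient meets the no-hypsarrhythmia condition at entry and becomes a complete responder on spasms alone.

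The cost is SAP wording and one consistency check of the Charter. No patients, visits or assessments are added.
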